### **9.3.2 Secondary Variables**

- Type of treatment regimen ( $\pm$  Dasabuvir,  $\pm$  RBV, intended and actual combination, dose and duration)
- Adherence
  - Percentage of the DAA dose taken in relation to the target dose of DAA (cumulative dose taken divided by target dose in percent)
  - Percentage of the RBV dose taken in relation to the target dose of RBV (cumulative dose taken divided by target dose in percent)
  - Percentage of missed RBV treatment days in relation to the target number of RBV treatment days
- Serious and non-serious adverse events and pregnancy occurrences
- Questionnaires on PROs: e.g. EuroQol 5 dimension 5 level (EQ-5D-5L) questionnaire and work productivity and activity impairment (WPAI) questionnaire prior to treatment initiation, at EoT as well as 12 and 24 weeks after EoT
- Questionnaire on healthcare resource utilization

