4.2 Statistical and Analytical Methods

4.2.1 Analysis Populations and Analysis Groups

Population of Patients Enrolled [EP]

The population of patients enrolled comprises all patients who voluntarily sign and date an informed consent prior to inclusion into the study and data were captured in the eCRF.

Target Population [TP]

Patients will be included if the following applies:

- Age at least 18 years
- Confirmed CHC with genotype 1 and/or 4 only, receiving combination therapy with the interferon-free ABBVIE REGIMEN \pm RBV. The prescribed ABBVIE REGIMEN needs to be known.
- Have voluntarily signed and dated an informed consent prior to inclusion into the study
- Must not be participating or intending to participate in a concurrent interventional therapeutic trial

Core Population [CP]

The core population is defined as all patients of the target population (TP) (definition see above), who are adequately treated according to the standard of care and within local label recommendations for their specific disease characteristics (cirrhotic status, genotype). The following patients will be excluded from the CP:

- Patients with unknown fibrosis status
- Cirrhotic patients with genotype 1a not receiving ribavirin
- Patients with genotype 1 for whom 2DAA instead of 3DAA is prescribed
- Patients with genotype 4 not receiving RBV

Non-Core Population [NCP]

Patients in the TP who are not in the CP.

Core Population with Sufficient Follow-up [CPSFU {12, 24}]

In addition, the core population with sufficient follow-up data regarding SVR12 or SVR24, respectively, is defined as all CP patients,

- who have evaluable HCV RNA data ≥ 70 days or >126 days, respectively, after the last actual dose of the ABBVIE REGIMEN
- or a HCV RNA value ≥ 50 IU/mL at the last measurement post-baseline
- or had HCV RNA <50 IU/mL at the last measurement post-baseline, but no HCV RNA measurement ≥ 70 days or >126 days, respectively, after the last actual dose of the ABBVIE REGIMEN due to reasons related to safety (e.g. dropped out due to adverse event) or virologic failure (e.g. virologic failure such as relapse is reported in the electronic case report form (eCRF) but date and value of the corresponding HCV RNA test is missing).

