For biopsy as assessment method the respective categories are defined as follows:

- “No cirrhosis” is defined by “No fibrosis”, “Mild/minimal fibrosis”, “Moderate fibrosis”
- “Transition to cirrhosis” is defined by “Advanced Fibrosis”
- “Cirrhosis” is defined by “Cirrhosis”.)

CP analysis groups and related treatment regimens

The CP analysis groups are defined according to the patient's fibrosis status and genotype/subtype. The standard summaries by CP analysis groups in the CP and CPSFU population are structured follows (is not specified otherwise):

- Total (regardless of cirrhosis status)
 - (1) Total (regardless of genotype)
 - (2) G1 (Total)
 - (3) G1a (including mixed subtypes and patients with unknown subtype)
 - (4) G1b
 - (5) G4 (non-G1)
- Patients with cirrhosis
 - (6) Total (regardless of genotype)
 - (7) G1 (Total)
 - (8) G1a (including mixed subtypes and patients with unknown subtype)
 - (9) G1b
 - (10) G4 (non-G1)
- Patients without cirrhosis
 - (11) Total (regardless of genotype)
 - (12) G1 (Total)
 - (13) G1a (including mixed subtypes and patients with unknown subtype)
 - (14) G1b
 - (15) G4 (non-G1)

SP analysis groups

The SP analysis groups are defined according to the treatment regimen and patient's fibrosis status. The standard summaries by SP groups in the safety population are as follows (if not specified otherwise):

- Total (regardless of cirrhosis status)
 - (1) Total
 - (2) 2DAA w/o RBV
 - (3) 2DAA + RBV
 - (4) 3DAA w/o RBV
 - (5) 3DAA + RBV
- Patients with cirrhosis
 - (6) Total
 - (7) 2DAA w/o RBV
 - (8) 2DAA + RBV
 - (9) 3DAA w/o RBV
 - (10) 3DAA + RBV
- Patients without cirrhosis
 - (11) Total
 - (12) 2DAA w/o RBV
 - (13) 2DAA + RBV
 - (14) 3DAA w/o RBV
 - (15) 3DAA + RBV
- Patients with unknown fibrosis status
 - (16) Total
 - (17) 2DAA w/o RBV
 - (18) 2DAA + RBV
 - (19) 3DAA w/o RBV
 - (20) 3DAA + RBV

(2DAA - paritaprevir/r-ombitasvir, 3 DAA - paritaprevir/r-ombitasvir + dasabuvir, RBV – ribavirin taken, w/o RBV – no ribavirin taken)

NCP analysis groups

The summary tables for the NCP will only show the data pooled for all patients in the NCP without any subgrouping by genotype and/or fibrosis status.

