- Key clinical chemistry and hematology laboratory variables at baseline
 - ALT ratio (continuous, see 4.2.6.5)
 - AST ratio (continuous, see 4.2.6.5)
 - Platelets [$10^9/L$] (continuous)
- Prior treatment status (HCV treatment naïve [reference], HCV treatment experienced)
- RBV vs no RBV
- Planned treatment duration 12 wks vs 24 weeks

The categories pre-specified above could be modified in the analyses if this is supported by the data (e.g. categories could be combined, if their impact on SVR12 is similar). Furthermore, continuous variables can be replaced by categorical variables.

Adherence

Adherence will be displayed for the CP by genotype and cirrhosis status and for the SP by treatment regimen and cirrhosis status. Summary statistics (n, mean, median, standard deviation [SD], and range) will be generated for continuous variable. Numbers and percentages of patients will be presented for categorical variables.

- Adherence to ABBVIE regimen (% of target dose [adherence=cumulated number of pills taken /(initial prescribed number of pills x planned duration)])
 - >105%
 - >95%-<=105%
 - >80%-<=95%
 - >50%-<=80%
 - <=50%
- Adherence to ribavirin (% of target dose [adherence=cumulated dose taken /(initial prescribed dose x planned duration)])
 - >105%
 - >95%-<=105%
 - >80%-<=95%
 - >50%-<=80%
 - <=50%

- Percentage of actual treatment duration in relation to the target duration of ABBVIE regimen taken
- Deviating duration of ABBVIE regimen
 - Early discontinuation (actual duration is shortened for more than 7 days)
 - Not deviated
 - Exceedance (actual duration is prolonged for more than 7 days)
- Method used to document adherence (Interview, Diary)
- Percentage of actual days with treatment with RBV in relation to the planned duration
- Ribavirin earlier discontinued than ABBVIE regimen
- Initial dose of Ribavirin
 - 1000 mg/day
 - 1200 mg/day
 - XXX
- Cumulative dose of Ribavirin (g)
- Dose modifications/termination of RBV [in patients taking RBV, for a patient more than one dose modification and its main reason could be reported, but for each single reason the patient is counted only once] (Total number of patients with lower dose than highest previous dose [including patients who stopped the treatment earlier], Anemia, Nausea/Vomiting, Rash, Other [including patients who discontinued ABBVIE regimen earlier, but did not stop the RBV treatment before the ABBVIE regimen])

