In addition to the summary statistics of the adherence variables, logistic regression analyses will be performed for the following adherence variables: "adherence to ABBVIE regimen" in all patients of the CP, "adherence to ribavirin" in all patients of the CP taking RBV, each categorized as follows: >=95%, >80%-<=95%, <=80% to investigate the additional impact of overall treatment adherence on SVR12. The categories may be changed if they are sparsely filled. Adherence will be included as mandatory covariate in addition to the baseline explanatory variables already mentioned above. Also the same methods will be applied as described above.

An overview of Tables is given in Table 7.

Table 7 Overview of Outputs for Primary and Secondary Effectiveness Analysis

Output Title	Output Short Name	Analysis Population
Virological Response Rates by Genotype and Cirrhosis Status – CP/CPSFU - <country>	tvr_<c>_gc_cp	Core population/ Core population with sufficient follow-up data
Virological Response Rates by Genotype and Cirrhosis Status in Patients who Completed ABBVIE Regimen – CP/CPSFU - <country>	tvr_<c>_gc_cp_ARC	Core population/ Core population with sufficient follow-up data: patients who completed ABBVIE regimen
Virological Response Rates - NCP - <country>	tvr_<c>_ncp	Non-core population
Relapse Rates by Genotype and Cirrhosis Status – CP - <country>	trr_<c>_gc_cp	Core population
Viral Breakthrough by Genotype and Cirrhosis Status – CP - <country>	tvb_<c>_gc_cp	Core population
Non-Response Rates by Genotype and Cirrhosis Status – CP - <country>	tnrr_<c>_gc_cp	Core population
Non-Response Rates by Genotype and Cirrhosis Status in Patients who Completed ABBVIE Regimen – CP - <country>	tnrr_<c>_gc_cp_ARC	Core population: patients who completed ABBVIE regimen
Impact of Patient and Disease Characteristics on SVR12 – CP - <country>	tis_<c>_cp	Core population
Adherence by Genotype and Cirrhosis Status - CP - <country>	tah_<c>_gc_cp	Core population
Adherence by Treatment Regimen and Cirrhosis Status - SP - <country>	tah_<c>_tc_sp	Safety population
Impact of Adherence to ABBVIE Regimen on SVR12 – CP - <country>	tiaa_<c>_cp	Core population
Impact of Adherence to Ribavirin on SVR12 in patients taking RBV – CP - <country>	tiar_<c>_cp_RBV	Core population: patients taking RBV

The layouts of the tables mentioned above are provided in Part II of the SAP (Table Shells).

4.2.7.2.2 *Quality of life*

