4.2.8 Analyses of Safety

All safety variables will be summarized for patients in the SP using descriptive statistical methods stratified by treatment regimen and cirrhosis status and overall.

An overview of tables for the individual values is given in Table 11.

The layouts of the tables mentioned above are provided in Part II of the SAP (Table Shells).

4.2.8.1 *Exposure to Study Medication*

One table will show the frequencies for early discontinuation and exceedance of ABBVIE regimen or ribavirin and the corresponding reasons for SP by treatment regimen and cirrhosis status. The ABBVIE regimen is considered to have been prematurely discontinued if actual duration is shortened for more than 7 days. The duration for taking ABBVIE regimen is considered to have been exceeded if the actual duration is prolonged for more than 7 days. Furthermore, summary statistics will be generated for the duration of ABBVIE regimen taken and the duration of ribavirin taken, i.e. n, mean, median, standard deviation [SD], minimum, maximum.

Unintended medication errors, i.e. patient missed taking Paritaprevir/r-Ombitasvir or Dasabuvir for at least 7 days in a row, will be displayed by medication for the entire treatment period.

4.2.8.2 *Co-medication*

Treatments, surgical and medical procedures will be coded by ABBVIE assigning appropriate preferred and class terms. Frequencies will be displayed for SP by treatment regimen and cirrhosis status.

In one table, the co-medication (preferred term) will be grouped by class. Only co-medication received during treatment specified by ABBVIE regimen will be displayed (Treatment profiles: A1, A2, C1 Drug B, C2 Drug B, C3 Drug B, D).

In another table, the co-medication (preferred term) will be grouped by profile. All treatment profiles will be considered, i.e.:

- A1: Continued (A1)
- A2: Permanently discontinued during CHC treatment (A2)
- A3: Permanently discontinued prior to CHC treatment (A3)
- B: Discontinued prior to CHC treatment and reintroduced post-treatment (B)
- C1 Drug A: Permanently replaced at start of CHC treatment (C1A)
- C1 Drug B: Substitute at start of CHC treatment and discontinued during CHC treatment (C1B)
- C2 Drug A: Permanently replaced at start of CHC treatment (C2A)
- C2 Drug B: Substitute at start of CHC treatment and continued (C2B)
- C3 Drug A: Replaced during CHC treatment (C3A)
- C3 Drug B: Substitute during CHC treatment (C3B)
- D: Introduced during CHC treatment (D)

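### For 3DAA patients, adherence to the regimen is one pill count pooled over two products, so omission of one product is understated, by up to one class in the SVR12 analysis

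*SAP*

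**What the plan says.** Protocol 9.3.2 lists one adherence percentage for the DAAs: "Percentage of the DAA dose taken in relation to the target dose of DAA (cumulative dose taken divided by target dose in percent". SAP 4.2.7.2.1 turns this into a pill ratio for the whole regimen: "adherence=cumulated number of pills taken /(initial prescribed number of pills x planned duration". Ribavirin has its own ratio.

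The regimen is one product or two, according to SAP 4.2.1: "2DAA - paritaprevir/r-ombitasvir, 3 DAA - paritaprevir/r-ombitasvir + dasabuvir". The same section removes from the core population "Patients with genotype 1 for whom 2DAA instead of 3DAA is prescribed", so every genotype 1 patient in the core population is prescribed both products.

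The logistic regression of SVR12 on adherence uses the regimen ratio and, in patients taking it, the ribavirin ratio, "each categorized as follows: >=95%, >80%-<=95%, <=80% to investigate the additional impact of overall treatment adherence on SVR12". SAP Table 7 lists one output for each. Neither DAA product has its own term.

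SAP 4.2.8.1 does look at the products separately. It defines an unintended medication error as a case where a "patient missed taking Paritaprevir/r-Ombitasvir or Dasabuvir for at least 7 days in a row, will be displayed by medication for the entire treatment period". SAP 4.2.8.3 and Table 11 also separate adverse events caused by medication error by product. These are descriptive outputs for the safety population.

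**The concern.** Secondary objective 2 in Protocol 8.2.2 asks how adherence influences treatment outcome. If a patient stops one product and continues the other, a pooled count falls only by the missing product's share of the tablets. It gives the same value to a patient who missed that many tablets spread over both products. Extra tablets of one product can also offset a gap in the other.

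The SAP treats the two products as separable elsewhere. It does not count a genotype 1 patient prescribed 2DAA as treated within the label, and it calls a week's gap in either product a medication error. Yet in the analysis that addresses objective 2, such a gap can be grouped with full adherence. That dilutes the contrast between adherence classes and affects the descriptive adherence tables in the same way.

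**Working it through.** The plan states no adherence figure to reproduce, so I apply the SAP formula directly.

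**Inputs**
- Planned duration T: the SAP covariate is "Planned treatment duration 12 wks vs 24 weeks".
- Regression classes (SAP 4.2.7.2.1): top ≥95%, middle >80% to ≤95%, lowest ≤80%. A value of exactly 95% fits both of the first two as written; I place it in the top class.
- Share s of the omitted product in the daily tablets: not in the documents. Assumed 1/3 to 1/2, with 1/4 to 3/4 as a wider range.
- Weeks w for which one product is omitted, everything else being taken as prescribed.

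**Formulas**
- Pooled adherence = 1 − s × w/T
- Adherence to the omitted product = 1 − w/T

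**12-week course**

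| Weeks omitted | Pooled, s = 1/3 | Pooled, s = 1/2 | Omitted product |
|---|---|---|---|
| 1 | 97.2% (top) | 95.8% (top) | 91.7% (middle) |
| 2 | 94.4% (middle) | 91.7% (middle) | 83.3% (middle) |
| 4 | 88.9% (middle) | 83.3% (middle) | 66.7% (lowest) |
| 12 | 66.7% (lowest) | 50.0% (lowest) | 0% (lowest) |

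The one-week row is the SAP's own threshold for a medication error. The pooled score stays in the top class there for any share up to 0.05 × 12 = 0.6.

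**Where the class changes.** The pooled score leaves the top class after 0.05 × T/s weeks and reaches the lowest at 0.20 × T/s. For the product itself these points are 0.05 × T and 0.20 × T. With T = 12:
- Product itself: 0.6 and 2.4 weeks.
- Pooled, s = 1/3: 1.8 and 7.2 weeks.
- Pooled, s = 1/2: 1.2 and 4.8 weeks.

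So the pooled score is one class too high from 0.6 to 1.8 weeks and again from 2.4 to 7.2 weeks (s = 1/3), or from 0.6 to 1.2 and from 2.4 to 4.8 weeks (s = 1/2). Outside those ranges the classes agree. On a 24-week course every boundary doubles: a one-week gap is then top class on both measures, and a four-week gap is middle class on both.

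A two-class error needs 1 − w/T ≤ 0.80 together with 1 − s × w/T ≥ 0.95, which requires s ≤ 0.05/0.20 = 1/4. Above that share the error never exceeds one class.

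**Sensitivity to the share.** Over s = 1/4 to 3/4, the 4-week omission on a 12-week course scores 91.7% to 75.0%. At s = 2/3 it scores 77.8%, the lowest class, so the shift in that example disappears.

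**Offsetting.** With s = 1/2, two weeks of one product missed plus a one-week extension of both gives (12 − 0.5 × 2 + 1)/12 = 100%. The products themselves score 11/12 = 91.7% and 13/12 = 108.3%. A 7-day extension does not count as exceedance under the SAP, which requires more than 7 days.

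**Information in the regression.** With 50 to 55 patients (SAP 3.2) and an assumed SVR12 of 90% to 97%, the expected number of failures runs from 50 × 0.03 = 1.5 to 55 × 0.10 = 5.5.

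**The case against.** A reader might infer that someone who omits a product for weeks is scored as nearly adherent, and that the SVR12 analysis cannot detect it. The documents do not support that. On a 12-week course the patient leaves the top class after 12.6 days (s = 1/3) or 8.4 days (s = 1/2). The 4-week case falls in the middle class, and complete omission falls in the lowest under either measure. What is lost is the size of the omission and the product concerned.

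A reader might also infer that pooling would explain a null adherence result. With about 1.5 to 5.5 failures expected, a null result is likely under either definition, and nothing in the documents shows how often one product alone is omitted.

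Other objections also carry weight:
- The protocol variable is itself one DAA percentage, so the SAP follows it.
- The examples depend on an assumed tablet share. If one product holds 1/3 of the tablets, the other holds 2/3, and for that one the 4-week shift vanishes.
- Adherence comes from interview (Protocol 9.4.1.2) or diary (SAP 4.2.7.2.1), which limits precision per product. The SAP's table shells, which might refine the derivation, are not in the documents.
- The analysis is exploratory, and its adherence classes may be changed if sparse.
- Nothing in the documents makes the lower of two product ratios the right main exposure.

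These points limit the finding to a sensitivity analysis and a stated limitation. They do not remove it: the ratio is pooled, no product-level term enters the SVR12 model, and the product-level gap display is not linked to outcome.

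**Conclusion.** The point holds in a limited form. For 3DAA patients, the pooled ratio understates omission of a single product and cannot identify which one was missed. At an assumed tablet share of 1/3 to 1/2, the understatement is at most one regression class, over limited ranges of omission. The clearest case on a 12-week course is a 7-day gap that the SAP itself calls a medication error but that lands in the top adherence class. Patients on 2DAA are unaffected because they take one product. The result rests on the assumed share, on all other tablets being taken as prescribed, and on reading the SAP formula as one count over both products, which is its natural reading. The study's main conclusions are not at risk. What improves is the descriptive adherence table and the answer to secondary objective 2.

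**What to change.** 1. Keep the pooled ratio as the protocol-defined measure, and state in the SAP and report that it understates single-product omission in 3DAA patients.
2. For 3DAA patients, add adherence to paritaprevir/r-ombitasvir and to dasabuvir as separate rows in the adherence tables, where the eCRF holds the counts by product.
3. Repeat the analysis of regimen adherence and SVR12 as a sensitivity analysis, using the lower of the two product-level values. If only pooled counts exist, use the by-medication flag for a gap of at least 7 days from SAP 4.2.8.1.
4. State the number of tablets prescribed per product, so that the dilution can be calculated instead of assumed.

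The cost is SAP wording, one derived variable per product, a few table rows and one more exploratory analysis, which will be imprecise because few SVR12 failures are expected. If the gap flag is used, no new data are needed.

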During the last decade, when dual therapy with pegylated interferon (pegIFN) plus RBV was standard of care for the treatment of CHC, the discovery of predictive factors for virological response and the subsequent development of treatment algorithms marked a milestone in patient care for CHC. As a consequence, treatment could be effectively targeted to patients most likely to respond. Interestingly, many of the now well established predictors of response to pegIFN/RBV and first generation direct acting antivirals (DAAs) in combination with pegIFN/RBV were not predictive of outcome in the development trials of the ABBVIE REGIMEN ± RBV. This observational study may play an important part in bridging the data gaps. It may help identify predictive factors of response that are important in real world treatment settings and thus, could assist in further optimizing treatment with the interferon-free ABBVIE REGIMEN ± RBV in the future.

The label of the ABBVIE REGIMEN ± RBV will vary according to hepatitis C virus (HCV) genotype/subtype and stage of liver disease. It is therefore relevant to understand the pattern of use and outcome in daily clinical practice. In addition, this study will provide data on the impact of adherence on treatment outcomes in everyday settings, which may help treating physicians to improve the management of patients under their care.

The main aim of this observational study is to provide evidence of the effectiveness of the ABBVIE REGIMEN ± RBV in a real world setting across clinical practice patient populations.

2 Study Objectives

The objectives of this study are:

Primary objective:

1. To describe in routine clinical practice the effectiveness of the interferon-free ABBVIE REGIMEN ± RBV in patients with CHC as evidenced by sustained virological response at 12 weeks after end of treatment (SVR12)

Secondary objectives:

2. To describe the pattern of real world use of the ABBVIE REGIMEN ± RBV with respect to different patient and treatment characteristics
3. To evaluate the influence of adherence on treatment outcome in routine clinical practice
4. To describe the tolerability of the ABBVIE REGIMEN ± RBV
5. To document the effect of the ABBVIE REGIMEN ± RBV on PROs and work productivity in the Dutch population
6. To determine the impact of the ABBVIE REGIMEN ± RBV on healthcare resource utilization

3 Study Design

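### Ribavirin adherence is scored against the initial prescribed dose, so the adherence model for SVR12 cannot separate missed tablets from dose changes ordered by the physician

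*SAP*

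**What the plan says.** One of the secondary objectives in SAP section 2 reads "To evaluate the influence of adherence on treatment outcome in routine clinical practice". Protocol 9.3.2 lists the RBV variable as "Percentage of the RBV dose taken in relation to the target dose of RBV (cumulative dose taken divided by target dose in percent" and does not say whether the target is the starting dose or the dose as later modified. SAP 4.2.7.2.1 settles this: "Adherence to ribavirin (% of target dose [adherence=cumulated dose taken /(initial prescribed dose x planned duration". The choice of the initial dose is therefore the SAP's.

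The same SAP section enters this ratio, for core-population patients taking RBV, as a mandatory covariate in a logistic regression on SVR12. It is "each categorized as follows: >=95%, >80%-<=95%, <=80% to investigate the additional impact of overall treatment adherence on SVR12". The SAP adds: "The categories may be changed if they are sparsely filled".

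The section also expects RBV doses to change. Its adherence table includes "Total number of patients with lower dose than highest previous dose", with reasons (anemia, nausea/vomiting, rash, other). It has further rows for RBV stopped before the DAAs and for the share of planned days on RBV. All of these are descriptive. None is named as a term in the adherence model.

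**The concern.** Adherence, in the sense of the objective, is whether the patient took what was prescribed. A ratio to the starting dose answers a different question: how much of the original plan was delivered. It falls for three reasons that it cannot tell apart: tablets missed, doses lowered or stopped on instruction, and a change in treatment duration.

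This matters because ordered changes are foreseeable. Protocol 7.1 attributes many adverse events and laboratory abnormalities in the earlier trials to RBV. Protocol 7.2 and SAP section 1 say that the adherence results may help physicians to improve patient management. An association between this ratio and SVR12 could come from patient behaviour or from tolerability-driven dose changes, and so could its absence. The model output alone would not show which.

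**Working it through.** The plan states no figure for this analysis, so there is none to reproduce. The check applies the SAP formula to a patient who takes every prescribed tablet.

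**Inputs**
- Score = dose taken / (initial dose × planned duration), from SAP 4.2.7.2.1.
- Model classes from the same section: ≥95%, >80% to ≤95%, ≤80%.
- D = 84 or 168 days (12 or 24 weeks, the planned durations).
- Fraction cut r and day of cut d are **assumptions**. The documents give neither the size, the timing nor the frequency of reductions. The values serve the arithmetic only and say nothing about dosing.

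**Formula**

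Score = [d + (D − d)(1 − r)] / D = 1 − r(1 − d/D).

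**Results for D = 84, all prescribed tablets taken**

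| Cut r | After day d | Score | Model class |
|---|---|---|---|
| 1/6 | 28 | 1 − (1/6)(56/84) = 88.9% | middle |
| 1/6 | 56 | 1 − (1/6)(28/84) = 94.4% | middle |
| 1/6 | 70 | 1 − (1/6)(14/84) = 97.2% | top |
| 40% | 28 | 1 − 0.4(56/84) = 73.3% | lowest |
| 40% | 56 | 1 − 0.4(28/84) = 86.7% | middle |
| 50% | 28 | 1 − 0.5(56/84) = 66.7% | lowest |
| 50% | 56 | 1 − 0.5(28/84) = 83.3% | middle |
| 50% | 77 | 1 − 0.5(7/84) = 95.8% | top |
| RBV stopped | 28 | 28/84 = 33.3% | lowest |

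**Where the classes change**
- The score falls below 95% when r(1 − d/D) > 0.05, that is, when d < D(1 − 0.05/r). For D = 84 this is before about day 59 for a one-sixth cut (84 × 0.70 = 58.8) and before about day 76 for a 50% cut (84 × 0.90 = 75.6).
- The score is ≤80% when r(1 − d/D) ≥ 0.20. A 50% cut lands there up to about day 50 (84 × 0.60 = 50.4). A cut below 20% never does, because r(1 − d/D) cannot exceed r.
- For D = 168, a one-sixth cut leaves the top class up to about day 118 (168 × 0.70 = 117.6). A 50% cut reaches the lowest class up to about day 101 (168 × 0.60 = 100.8).

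**Same score, different behaviour**
- Patient A: 50% cut after day 28, nothing missed: (28 + 56 × 0.5)/84 = 66.7%.
- Patient B: no cut, 28 of 84 days missed: 56/84 = 66.7%.

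**With the denominator set to the dose prescribed on each day**
- Patient A: (28 + 28)/(28 + 28) = 100%.
- Patient B: 56/84 = 66.7%, unchanged.

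The two patients now separate.

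**The case against.** **Dose against the original plan is a legitimate measure.** This stands. Protocol 9.3.2 separately lists intended and actual dose, so reading the target as the originally intended dose is natural, and the SAP prints its formula openly. A measure against the current prescription would score a patient whose RBV was stopped on instruction as fully adherent and lose the reduced exposure. That is a reason to report both, not to discard the present ratio.

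**The SAP already shows dose changes.** This holds for the tables: modifications by reason, early RBV stops and cumulative dose let a reader judge at group level. It does not repair the regression, where none of these is a term. The row for days on RBV is unaffected by a reduction, but it divides by planned duration, so an ordered stop still counts against the patient.

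**The data may not support the alternative.** This partly stands. Modifications are recorded, but the documents do not show that dated prescribed doses are held separately from doses taken. Adherence comes from interview (Protocol 9.4.1.2) or diary (SAP 4.2.7.2.1).

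**Little is at stake numerically.** This stands. The study expects 50–55 patients, and the number on RBV is not given. The overall with-RBV SVR12 rates cited in Protocol 7.1 run from 92% to 100%. If all 55 took RBV and 92% responded, there would be 55 × 0.08 = 4.4 failures, plus any missing results counted as failures. A three-class covariate is barely estimable with either denominator.

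**Stronger readings that the documents do not support.** A reader might infer that every compliant patient with a reduction is classed as non-adherent. The SAP has no such class, only bands of percent of target dose, and small or late cuts stay in the top band. A reader might also infer that the model measures dose reduction, or mainly contrasts reduced with unreduced patients. The ratio is a mixture, and nothing in the documents says how common reductions or missed tablets are.

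**Conclusion.** The concern holds for the regression. The RBV ratio cannot distinguish missed tablets from ordered reductions or stops, and it is the only RBV adherence term in the model for the adherence objective. In the illustrations, a patient who takes every prescribed tablet over 84 days scores anywhere from 33.3% (RBV stopped after day 28) to 97.2% (one-sixth cut after day 70). The spread depends entirely on the assumed cut, and its frequency in this cohort is unknown. The effect is on what one exploratory secondary output can be said to show. It is worth correcting because the correction is cheap, but it does not touch the primary SVR12 estimate.

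**What to change.** 1. Keep the present ratio and label it *RBV dose intensity versus initial plan*.
2. Add *RBV adherence* = dose taken / dose prescribed, both summed over the days on which RBV was prescribed. Use this in the adherence model for SVR12, with dose intensity reported alongside.
3. If dated prescribed doses are incomplete, use missed RBV days over days on which RBV was prescribed. Missed RBV days are already a listed variable (Protocol 9.3.2, SAP 4.1.2). If that also fails, relabel the model output as dose intensity and state that it does not isolate patient compliance.
4. In the same edit, remove the overlap at exactly 95%, which now belongs to both the top and the middle model class. The descriptive bands start the corresponding category above 95%.

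**Cost:** SAP wording and one derived variable. The new measure depends on complete modification dates, and it does not cure the small number of events, so the model stays exploratory.
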